## ABBREVIATIONS

AE	Adverse Event
DSM	Data Safety Monitoring
DSMB	Data Safety Monitoring Board
DSMC	Data Safety Monitoring Committee
DSMP	Data Safety and Monitoring Plan
DSO	Data and Safety Officer
DQA	Director of Quality Assurance
GCP	Good Clinical Practice
ID	Infectious Disease
IIS	Investigator Initiated Protocol
IRB	Institutional Review Board
NGS	Next Generation Sequencing
OSP	Office of Sponsored Programs (UT HEALTH)
QAD	Quality Assurance Division
PI	Principal Investigator
SAE	Serious Adverse Event
SOC	Standard of Care
UPIRSO	Unanticipated Problem Involving Risks to Subjects or Others
UT Health	University of Texas Health Science Center at San Antonio

[figure not shown]

## 1.0 STUDY SYNOPSIS

This is a randomized controlled clinical study evaluating the use of next-generation sequencing (NGS) to improve antibiotic prescribing before ureteroscopy or percutaneous nephrolithotomy. NGS will be performed on voided urine collected as routine care approximately 30 days prior to surgery. Results will be presented to ID pharmacist within 48-72 hours to help select the most appropriate antibiotics, and independently as part of routine care, surgeons will choose the antibiotic that they would use in each case, while the ID pharmacists would select their optimum choice. Pharmacists will account for site-specific antibiotic stewardship practices, allergies, medication adjustments, and C. difficile rates. Approximately 300 subjects will be randomly assigned in a 1:1 ratio to receive either NGS antibiotic recommendation or standard of care (SOC) prophylaxis prescribed treatment. All providers within the Department of Urology who perform urologic stone procedures (n=5) will also be approached in person with an information sheet. Subjects assigned to standard of care will have urine cultures sent for analysis, and the physician will choose antibiotics based on results as per usual practice. Subjects assigned to the NGS group, in addition to routine urine culture results, will have NGS urine culture results sent to an ID pharmacist, and recommendations will be shared with the physician to determine the antibiotic selection. The physician will ultimately decide the appropriate antibiotics to prescribe. Approximately 7-14 days after surgery, the research staff will conduct a telephone call to ask about any post-operative infections, complications, and any additional antibiotics that were prescribed.

**Figure 1: Study Schema**

## 2.0 BACKGROUND AND SIGNIFICANCE

Antibiotic selection before surgery is usually left to the surgeon to make the best selection; however, there is considerable variation noted in antibiotic prophylaxis. The American Urological Association published a Best Practices white paper; however, a large proportion of surgeons continue to not abide by recommendations. Efforts are needed to reduce variation from recommended antimicrobial prophylaxis for common urological procedures to reduce antibiotic adverse events and complications.

The benefit of antimicrobial prophylaxis has been shown in multiple studies; however, some countries do not use antibiotic prophylaxis and have comparable infection rates. Prophylactic antibiotics should be effective against an organism's characteristic of the operative site with excellent safety profiles in short duration. The most common antibiotics utilized in urologic endoscopic surgery are cephalosporins, fluoroquinolones, and aminoglycosides. These antibiotics are usually used in short duration, but recently a rise in antibiotic resistance has led to increased risk of infection. The escalation of one or multiple broad-spectrum could be related to health policy changes indicating that insurance companies would not pay for readmission for infectious complications after surgical procedures. Surgeons are then utilizing more antibiotics or antibiotics that should be reserved for significant infections and not necessarily prophylaxis.

Ureteroscopy for urinary tract urolithiasis is a common procedure with an estimated 9,200 cases in the US per year. However, the incidence of systemic inflammatory response syndrome (SIRS) after flexible ureteroscopic (URS) lithotripsy is 7.1%, despite the use of recommended antibiotic prophylaxis. Obtaining a urine culture prior to surgery is standard of care, and physicians start culture-specific antibiotic treatment on patients with a positive culture—and preferably found to be negative on repeat culture—before their urologic stone procedure. One of the challenges when choosing a prophylactic agent is that preoperative urine cultures often show no growth for patients who later develop SIRS. Singh *et al.* found no significant association between pelvic urine cultures or stone cultures and the occurrence of SIRS. We hypothesize the stone or previously placed stent may allow bacteria to form biofilms or not detected by standard cultures.

Next Generation Sequencing (NGS) technology could assist physicians in selecting antibiotic prophylaxis therapy before surgery in patients that have a normal urine culture. Urine culture is a technique that utilizes specialized agar to select the bacterial presence in a fluid. Issues with standard culture are that one must use a priori select particular groups of bacteria and assume they would grow on the plate, which requires the bacteria to be at a certain concentration. NGS testing can use the combination of PCR and 16sRNA to identify the bacterial presence and does not discriminate by growth patterns and are not limited by bacterial counts. NGS can also identify fungal species, which require a separate technique when using standard culture. Our proposal focuses on the identification of high-risk cases and antibiotic prophylaxis patterns and how NGS can assist with antibiotic prophylaxis decision making. Anticipating the use of NGS may have unintended consequences, we address issues with implementation and how to establish an interpersonal healthcare approach to abide by antibiotic stewardship programs.

We performed NGS and PCR for common resistance genes in subjects prior to ureteroscopy. Of the urine being sent for culture, approximately 5-10mL was sent to Microgen Dx for the analysis. NGS results were blinded to the physician, and analysis was done after surgery. Surgery, as scheduled per the physician and prophylaxis antibiotics, were prescribed as the standard of care. After the surgery, we made 3 case studies that were reviewed by board-certified Urologists to determine if they would change their prophylactic antibiotic regimen and what antibiotic they would prescribe. Two infectious disease pharmacists also reviewed the case reports and provided the “ideal” antibiotic regimen to be prescribed.

After IRB approval, we obtained samples from urine specimens already provided as a preoperative urine culture from twenty patients scheduled for urologic stone surgery. Two cultures returned positive with Enterococcus, and the NGS result was the same. One sample had two species (enterococcus and coagulase-negative Staphylococcus), in which NGS was able to find both organisms and speciated the staphylococcus to

be *Staphylococcus epidermidis*. Of the 18 cultures with no growth, 56% (10/18) did show a dominant-bacteria on NGS. Eight urologists returned the three case scenarios, and in each of the 3 cases 100%, 88%, and 88% of the physicians would have prescribed a different prophylaxis antibiotic given these results. The ideal antibiotic of choice based on the ID Pharmacist is oral Bactrim for all cases, and only 50%, 0%, and 0% selected this option, and 38%, 25%, and 63% chose to escalate the antibiotic to vancomycin, Zosyn, or amikacin in conjunction with a second antibiotic. Overall on the exit survey urologists feel it is moderately important (n=2, 25%), important (n=4, 50%), or very important (n=2, 25%) to test this technology in this context and 38% have concerns about using this technology for antibiotic prophylaxis.

[figure not shown]
NGS may be more effective and specific than those predicated upon SOC preoperative urine cultures mostly negative before surgery. For example, we identified several culture negative patients with dominant bacterial types that may influence a physician to prescribe a 1st generation cephalosporin compared to a gram-negative dominant group that may need a fluoroquinolone or 3rd generation cephalosporin. Importantly, urologists do not typically send a urine specimen specifically for fungi (*Candida* sp.). The PCR/NGS test readily makes this information available and in one patient that was positive did have sepsis caused by *Candida*, which was later cultured from the patient's blood. Many studies have reported the low sensitivity of preoperative urine cultures for predicting infectious complications of urologic stone procedures.

Eswara et al. (2013) compared sensitivities among preoperative and perioperative pelvic urine and stone cultures for pathogen detection, reporting that of the patients who develop urosepsis, 0% had positive midstream preoperative urine cultures, while 73% had positive stone cultures. However, they report a 64% concordance rate in urosepsis patients between stone cultures and readmission cultures, indicating that stone cultures did not always appropriately guide antibiotic selection in up to 36% of cases. Moreover, an antibiotic selection from stone culture rarely is provided in a timely fashion to alter postoperative antibiotics, and many of our patients go home the same day of the procedure. Our study, while small, found that NGS was able to detect pathogens and provide alternate antimicrobial prophylaxis, especially in those who did have an infection.

Our findings are consistent with those of Long et al. (2016) and Grumaz et al. (2016), who reported that NGS is more sensitive than blood cultures for detecting pathogens in ICU patients. Notably, their studies observe the clinical utility of NGS to guide therapy in a high-risk population of ICU patients. Many studies have reported the increased sensitivity of NGS when compared to cultures, but further research is needed to establish cases where the improved sensitivity delivers cost-effective, clinically applicable data. The results of this study suggest that NGS may improve the standard of care in patients undergoing invasive urologic stone procedures.

Infectious complications are the most common cause of death following urologic stone procedures and present a sizeable economic drain on the American healthcare system. Other studies have found that up to 17% of urosepsis cases follow urologic interventions. Koras et al. (2014) observed signs of SIRS in up to 27% of patients who underwent PCNL, 7.6% of which were diagnosed with sepsis. Given the mortality rates and economic costs of urosepsis, SOC practices must be optimized to reduce the risk of infectious complications following urologic procedures.

NGS identifies a targetable bacterium in up to 50% of negative urine cultures prior to urologic stone surgery. Many physicians chose to escalate IV antibiotics rather than utilized oral medications. Therefore, working with an infectious disease pharmacist may be helpful in guiding the selection and operating room availability of

**Figure 2:** Preliminary results from NGS compared to standard urine culture prior to urologic surgery.

antibiotics based on NGS results to improve antibiotic stewardship. Larger long-term studies are needed to determine if this strategy will lead to reduced infection rates.

### **3.0 SPECIFIC AIMS**

#### **Specific Aim 1: To perform a randomized clinical trial investigating the use of NGS for antibiotic selection to lower post-operative infection rates over the standard of care.**

*Hypothesis: utilization of NGS for the selection of preoperative antibiotics reduces postoperative infection rates by 75%. Our baseline rate of infection was 11-15% in our pilot study and nearly 5-10% in our investigation of those ureteroscopies (not PCNL, which has a higher rate) of infections at a university hospital. We expect with the correct antibiotics that the infection rate may drop from 11% to 1% or less. The control arm will be utilized to determine if NGS may have predicted infections or high-risk groups. Retrospective databases include anywhere from 2-15% of patients will present with a postoperative infection after transurethral surgery. Current prophylaxis strategies do not always follow guidelines, and with concerns over current non-reimbursement for infectious complications, surgeons may be using more antibiotics.*

**Specific Aim 2: Accuracy of NGS and PCR compared to standard urine culture prior to transurethral procedures.** *Hypothesis: NGS can identify 50% of negative urine cultures that could harbor uropathogenic bacteria.* We anticipate a substantial number of patients have uropathogenic bacteria present yet are not detected by traditional approaches. We seek to expand our investigation on this topic in order to understand how best to interpret the results and present them to physicians. All participants will have both a standard of care urine culture and NGS testing/ID Pharmacy review for comparative analysis. Only subjects assigned to the NGS group (n=110) will have NGS urine culture results and ID Pharmacist recommendations shared with the physician to determine antibiotic selection. Operating characteristics to include sensitivity, specificity, positive, and negative predictive value will then be performed and area under the receiver operative curve calculated. We will enroll a minimum of 250 patients and 5 urology provider-participants into this study. We anticipate that 20 of the patients will have positive urine cultures and 200 will have negative cultures. Of the 200 negative cultures we anticipate that 100 (50%) will harbor uropathogenic bacteria which will be identified via NGS.

**Specific Aim 3: To investigate the influence of Next Generation Sequencing (NGS) on physician prophylactic prescribing habits in patients with a negative preoperative urine culture.** *Hypothesis: NGS will cause any antibiotic change in prophylaxis in 50% of cases.* Based on preliminary data, we identified that over 80% of physicians would change their antibiotic for surgery if given this information. However, we anticipate surgeons will use an antibiotic escalation approach compared to a pharmacist's selected optimum prophylaxis antibiotic approach. Therefore, the control arm will receive standard of care antibiotics compared to the intervention group. The intervention group will get three levels of information: (1) standard of care culture, (2) full NGS report, and (3) infectious disease pharmacist recommendations based on NGS. The physician will then utilize these tools to select the best antibiotic for the case.

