### **4.0 RESEARCH PLAN AND DATA COLLECTION**

The goal of this proposal is to evaluate if the use of NGS on preoperative antibiotic selection reduces postoperative infection rates over the standard of care. Patients scheduled to receive a transurethral procedure, such as a ureteroscopy or percutaneous nephrolithotomy (PCNL), will be approached for enrollment prior to their procedure. After informed consent has been obtained, approximately 5-10 mL of left-over urine, collected for a standard of care urine culture, will be obtained for research and sent to MicroGen Dx for NGS. Patients will be randomized to receive either standard of care culture results (only), versus NGS results and Infectious Disease (ID) Pharmacist antibiotic recommendation. The physician will utilize these results to select the best antibiotic for the case but is not required to abide by the ID pharmacist's recommendation. The standard of care group will also have a urine sample sent to MicroGen Dx, but the results will not be provided to the physician. All subjects enrolled will receive a standard of care culture as part of routine care. A chart review and/or telephone follow up will be completed approximately 7-14 days post urologic procedure to assess for complications, infections related to the procedure, and antibiotics prescribed.

The treating physicians will have control over antibiotic administration. Their determination, interaction, and ultimately patient outcome will be documented and evaluated. As a result, the treating physicians will be considered participants in this study. A waiver of documentation of informed consent for the treating physicians will be included. In addition, an information sheet will be provided to treating physicians specifically.

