### **10.0 METHOD OF ANALYSIS/STATISTICS**

**Next Generation Sequencing:** Standard of care whole urine will be collected (approximately 30-50 mL) utilizing special vacutainers supplied by MicroGen Dx. Approximately 5-10mL of urine taken for culture will be sent to MicroGen Dx, a CAP-accredited and CLIA licensed clinical diagnostic lab, for analysis. MicroGen Dx will perform rapid PCR for common resistance genes prior to ureteroscopy or percutaneous nephrolithotomy. The plan will be to run target bacterial or fungi DNA on the quantitative PCR (qPCR) panel assay on the Roche LightCycler 480 II instrument and sequencing of 16S ribosomal RNA hypervariable regions V1-V2 using Ion Torrent (Ion Torrent PGM).

**Microbiome:** Sequencing reads were demultiplexed using QIIME2 software and denoised using dada2 software, using a phred score threshold of 28. Alpha diversity will be measured using the Shannon index, and a Wilcoxon test was used to determine whether the Shannon index differed between patients with stents and those without stents at the time of urine collection. Principle coordinates analysis (PCoA) of Bray-Curtis dissimilarity will be performed to visualize differences in species composition between patients with and without stents, and Linear discriminant analysis Effect Size (LEfSe) analysis was conducted to identify differentially abundant taxa between stent and non-stent groups.

**Sample size:** This will be a randomized trial of Microgen Dx versus standard of care. The primary endpoint is infection within 14 days of surgery. The primary objective of the study is to evaluate whether Microgen Dx reduces an infection rate compared to the standard of care. The null hypothesis is that infection rates within 14 days of surgery are the same between the randomization arms. The alternative hypothesis is that infection

rates within 14 days of surgery are not equal between the randomization arms. The infection rates are assumed to be 11% in the control arm and 1% in the experimental arm based on our preliminary data. A sample size of 85 per group will give 80% power to detect a 10% difference in infection rate when the two-sided Z-test with alpha=0.05 is used. Demographics and potential confounding factors will be summarized by randomization arm. A logistic regression model will be used to measure the association between the primary outcome and treatment arm with adjustment for the observed covariates.

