**Statistical analysis:** Our primary outcome is infection after surgery as a dichotomous outcome. We will utilize a chi-squared analysis to determine the difference between intervention and control groups. We will assess demographics between groups using chi-squared for dichotomous variables and Student's t-test for continuous variables. Additionally, we will investigate the utilization of antibiotic in a mixed-model regarding a number of antibiotics and antibiotic class utilization.

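### The assumed fall from 11% to 1% needs at least 91% of infections to lie in the half of patients whose antibiotic NGS is expected to change; the plan does not state this and plans no infection comparison by NGS status

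*Combined protocol and SAP*

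**What the plan says.** - **Assumed effect (Section 3.0, Aim 1, and Section 10.0, Sample size).** Aim 1: "We expect with the correct antibiotics that the infection rate may drop from 11% to 1% or less". Section 10: "The infection rates are assumed to be 11% in the control arm and 1% in the experimental arm". The same Aim 1 paragraph also hypothesises that the strategy "reduces postoperative infection rates by 75" per cent.
- **Sample size (Section 10.0).** "A sample size of 85 per group will give 80% power to detect a 10% difference in infection rate". Section 8.4 randomises 110 per group, Section 8.0 speaks of 250 completers, and the synopsis of about 300 subjects.
- **Population (Sections 4.0 and 5.0).** Any consenting adult having stone or other transurethral surgery is eligible. There is no selection on culture or NGS result.
- **How often NGS finds something (Aim 2).** "Of the 200 negative cultures we anticipate that 100 (50%) will harbor uropathogenic bacteria which will be identified via NGS". Another 20 patients are expected to be culture-positive.
- **How often NGS changes treatment (Aim 3, culture-negative patients).** "NGS will cause any antibiotic change in prophylaxis in 50% of cases". Aim 3 also reports that over 80% of physicians would change. That figure comes from the pilot in Section 2.0, where eight urologists read three case scenarios. Under Section 4.0 the physician may set the advice aside.
- **NGS in both arms (Section 4.0).** "The standard of care group will also have a urine sample sent to MicroGen Dx"; the results are withheld from the physician.
- **Infection analysis (Section 10.0).** "We will utilize a chi-squared analysis to determine the difference between intervention and control groups", plus a covariate-adjusted logistic regression by arm. Aim 1 adds that control-arm NGS results will be examined as a predictor of infection or of high-risk groups; Section 10 gives no method for this.

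**The concern.** NGS can prevent an infection only by altering what is prescribed. If about half of patients receive the antibiotic they would have had anyway, that half adds events to both arms and no difference between them. The whole-arm effect then depends on how infections divide between patients whose treatment changes and patients whose treatment does not. The plan assumes a 10-point whole-arm effect without saying what division it relies on.

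Two things are at stake. The 80% power may be far from the real figure if infections are less concentrated than 11% to 1% requires. And a small or null all-comer difference would be hard to interpret: the strategy might do little for anyone, or it might work in patients with an NGS-only finding while few infections arise there. Both arms have NGS before surgery, so the data to explore this will exist, but no between-arm infection analysis using them is planned.

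**Working it through.** **1. The plan's own figure.** Two-sided alpha 0.05, 80% power, 11% against 1%, unpooled variance:

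n = (1.960 + 0.842)² × (0.11×0.89 + 0.01×0.99) / 0.10² = 84.6, so 85 per group. The stated figure reproduces. The pooled formula gives 88, and power 78.9% at 85 per group. The powers in steps 3 to 5 use the pooled Z-test.

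**2. Concentration needed for 1%.** Let *s* be the share of control-arm infections that fall in patients whose antibiotic would change, and *e* the fraction of those prevented. Assume that an unchanged antibiotic leaves risk unchanged. Then

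NGS-arm rate = 11% × (1 − s·e).

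Setting this to 1% gives s·e = 10/11 = 90.9%. Since *e* cannot exceed 1, *s* must be at least 90.9%. If the changed group is half of patients, control risk would be 10%/0.5 = 20% in that half and 1%/0.5 = 2% in the other, a ten-fold ratio.

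**3. Illustration: infections spread evenly, all prevented in the changed group.** Here *s* equals the changed share and *e* = 1.

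| Changed share | Source | NGS-arm rate | Power, 110 per arm |
|---|---|---|---|
| 45% | 100/220 (Aim 2) | 6.0% | 26% |
| 50% | Aim 3 | 5.5% | 32% |
| 55% | 120/220, adding culture-positives | 5.0% | 37% |
| 60% | pilot, 12/20 with any finding | 4.4% | 45% |
| 80% | physician figure read as a patient share | 2.2% | 75% |
| 88% | lower scenario figures in the pilot, read the same way | 1.3% | 85% |

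No row reaches 1%. For 11% against 5.5%, power is 25% at 85 per arm, 35% at 125 and 41% at 150; 80% power needs 392 per arm.

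**4. Intermediate concentration, complete prevention.**

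- s = 70%: 3.3%; 175 per arm for 80% power.
- s = 75%: 2.75%, which equals Aim 1's own 75% reduction; 147 per arm. Power is 57% at 85, 68% at 110 and 81% at 150.
- s = 80%: 2.2%; 124 per arm.

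**5. What an analysis by NGS status could show.** Take 110 per arm and 100/220 culture-negative/NGS-positive, so 50 per arm in the subgroup and 60 outside it.

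- *Equal risk, 11% to 1% in the subgroup only.* Whole-arm NGS rate = (120/220)×11% + (100/220)×1% = 6.45%; all-comer power 22%. In the subgroup, Fisher's exact test has about 35% power. The uncorrected chi-squared test shows 60%, but with about 5.5 against 0.5 expected events it should not be relied on.
- *Two-fold risk in the subgroup.* Risk outside = 11%/(1 + 100/220) = 7.6%; inside 15.1%. With 10/11 of subgroup infections prevented, 15.1% falls to 1.4% and the whole-arm rate is 4.75%. All-comer chi-squared power is 42%. In the subgroup Fisher's exact power is about 59%, against 77% for the uncorrected test.
- *Interaction on the risk-difference scale, normal approximation.* Power is about 27% in the first case and 48% in the second.

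**The case against.** **The 50% is a hypothesis, not a cap.** It concerns any change in culture-negative cases, and the over-80% figure stands beside it. This is right, so the result is conditional. The 80% figure, however, counts physicians reading scenarios rather than patients; read generously as a patient share, it still leaves 2.2%.

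**Concentration is the trial's rationale.** Section 2.0 notes that cultures often show no growth in patients who later develop a systemic inflammatory response, and that in the pilot NGS offered alternatives particularly for those who became infected. Even spread may well be too pessimistic. But no document says what share of infections occurs in NGS-positive patients.

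**All-comers is the right comparison.** NGS must be ordered before its result is known, so dilution is part of the strategy's true effect, and an unselected population is a legitimate choice. This stands in full. A reader might infer that a null all-comer result would not count against NGS-guided selection. The documents do not support that: Section 4.0 asks whether using NGS lowers infection rates, and the whole-arm comparison answers it.

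**The plan does look at these patients.** A reader might infer that nobody examines those NGS could help. That goes too far: Aim 1 uses the control arm to see whether NGS predicted infection, and Aim 3 studies prescribing in culture-negative patients. What is missing is narrower: a between-arm comparison of infection by NGS status, and a method for the control-arm question.

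**The subgroup is imperfect and small.** Culture-negative/NGS-positive status is not the same as a changed antibiotic. A negative report, resistance genes, fungal findings or pharmacist advice may also alter prescribing, and physicians may leave it unaltered after a positive report. With about 50 per arm the analysis can only be supportive.

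**Conclusion.** The point holds as a conditional. If NGS changes the antibiotic in about half of patients, and an unchanged antibiotic leaves risk unchanged, then 11% to 1% requires at least 91% of infections in that half and complete prevention there. The plan neither states nor supports this. It is tempting to conclude that 1% is impossible, or that 5.5% to 6.0% is a floor. Neither follows: those rates rest on an even spread of infections, which the documents do not assert and the rationale argues against.

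The consequence for power is material. Under even spread at a 50% changed share it is about 32% at 110 per arm; at the plan's own 75% reduction it is 68% at 110 and 57% at the stated 85. The missing comparison by NGS status is a real but modest gap, since it could inform interpretation but not confirm an effect. Both points should be dealt with before outcomes are seen; neither calls for a different primary comparison or population.

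**What to change.** 1. **Primary.** Keep the all-comer comparison as primary and as the answer to the strategy question. Report a null result as such, with the subgroup result alongside it and not in place of it.
2. **Aim 1 and the sample-size paragraph.** State the share of infections, and the fraction prevented, that 11% to 1% relies on. Add a short table of NGS-arm rate and power at lower concentrations. Reconcile the 75% reduction with the fall to 1%.
3. **Section 10.** Add a prespecified supportive secondary analysis: infection within 14 days by randomised arm in culture-negative/NGS-positive patients. Classify status from the pre-surgery report by someone unaware of arm and outcome. Give the risk difference with confidence interval and an arm-by-NGS-status interaction, using exact or other small-sample methods. Label it not confirmatory and low-powered (about 50 per arm; Fisher's exact power about 35% for 11% against 1%, about 59% if subgroup risk is two-fold).
4. **Subgroup definition.** Do not define it by actual antibiotic change. That arises after randomisation and, for a change caused by the NGS report, has no counterpart in the control arm.
5. **Control-arm question.** Give a method for Aim 1's look at whether NGS predicted infection.

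Cost: text changes and one extra analysis on data already to be collected in both arms, with no additional patients or tests. The price is a less favourable stated expected effect and one more low-powered result to report with care.

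### Aim 2 implicitly scores NGS against urine culture, which the plan itself says misses uropathogens, so meeting the aim's hypothesis would be reported as 50% specificity

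*Combined protocol and SAP*

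**What the plan says.** Section 3.0 heads Specific Aim 2 "Accuracy of NGS and PCR compared to standard urine culture prior to transurethral procedures". Every participant is to have both tests, and the paragraph then commits to accuracy statistics: "Operating characteristics to include sensitivity, specificity, positive, and negative predictive value will then be performed and area under the receiver operative curve calculated".

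The same paragraph gives the premise that culture is incomplete: "We anticipate a substantial number of patients have uropathogenic bacteria present yet are not detected by traditional approaches". It expects 20 positive and 200 negative cultures, and adds: "Of the 200 negative cultures we anticipate that 100 (50%) will harbor uropathogenic bacteria which will be identified via NGS".

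Section 10.0 has no Aim 2 analysis. It covers the assay, microbiome diversity, the infection endpoint with its sample size, group comparisons and a model of antibiotic use. Sections 4.0 and 10.0 describe a quantitative PCR panel and 16S sequencing. Neither gives an organism list or threshold that makes a sample NGS-positive, and no variable is named for the ROC curve.

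**The concern.** Sensitivity, specificity and predictive values treat the comparator as the truth. The aim's premise is that this comparator is wrong in a large share of the patients it calls negative. Each extra organism that NGS finds, which is what the investigators hope for, therefore lowers its reported specificity and PPV.

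The conflict is exact. The hypothesised quantity is the proportion NGS-positive among culture-negatives. Specificity against culture is one minus that proportion. The better the hypothesis does, the worse the accuracy looks.

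Aim 2 is meant to show how NGS results should be read and conveyed to physicians. A headline of 50% specificity and a PPV under 20% would mislead on that question. With no written positivity rule, the cut-off could also be chosen after the results are seen, and both the hypothesised 50% and the specificity depend on it.

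**Working it through.** **Inputs (Section 3.0, Specific Aim 2).** 20 culture-positive; 200 culture-negative; 50% of the culture-negatives NGS-positive. NGS detection among the 20 culture-positives is not stated, so it is varied below.

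**The plan's figure.** 0.50 × 200 = 100 NGS-positive among culture-negatives, as stated.

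**Culture as reference.** False positives (FP) = 100; true negatives (TN) = 200 − 100 = 100; true positives (TP) at most 20. Intervals are exact (Clopper-Pearson).

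- Specificity = TN/(TN + FP) = 100/200 = 50.0% (95% CI 42.9% to 57.1%).
- PPV = TP/(TP + FP), at most 20/120 = 16.7% (10.5% to 24.6%).
- AUC of a two-level call = (sensitivity + specificity)/2, at most (1 + 0.5)/2 = 0.75.

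| NGS detects, of 20 culture-positives (assumed) | Specificity | PPV | NPV | Two-level AUC |
|---|---|---|---|---|
| 20 | 50% | 20/120 = 16.7% | 100/100 = 100% | 0.75 |
| 16 | 50% | 16/116 = 13.8% | 100/104 = 96.2% | 0.65 |
| 10 | 50% | 10/110 = 9.1% | 100/110 = 90.9% | 0.50 |

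Specificity does not depend on the assumption. The 0.75 ceiling applies only to a detected/not-detected call; a graded measure, which the quantitative PCR might supply, has no such ceiling.

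**Pilot (Section 2.0).** 10 of 18 no-growth cultures had an NGS finding. The same scoring gives specificity 8/18 = 44% (22% to 69%).

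**Total.** 20 + 200 = 220, which matches 2 × 110 in Section 8.4 but not the minimum of 250 in the same paragraph. The 50% is a ratio within culture-negatives and does not depend on this.

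**The same data as a paired comparison.** If NGS finds every culture-positive, detection is 120/220 = 55% by NGS and 20/220 = 9% by culture. Discordant pairs are b = 100 and c = 0. The difference is 100/220 = 45.5 points, with SE = √(100 − 100²/220)/220 = 0.0336 and 95% CI 38.9 to 52.0. If NGS misses 2 of the 20 (c = 2), the difference is 98/220 = 44.5 points (37.7 to 51.4).

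**Events for an exploratory control-arm analysis.** Culture-negative controls: 110 × 200/220 = 100. If their infection rate equals the overall rate (an assumption), 11% gives about 11 infections, and the 2% to 15% range in Aim 1 gives 2 to 15. As an illustration only, suppose 50 of the 100 are NGS-positive and 9 of the 11 infections fall among them. Sensitivity is then 9/11 = 82% (48% to 98%), infection is 9/50 = 18% against 2/50 = 4%, and Fisher's p = 0.051.

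**The case against.** **The heading already makes culture the reference.** This stands. A reader might infer that Aim 2 has no reference at all, but the documents do not support that: culture is the only comparator named, and patients are counted by culture result. The defect is that the implied reference conflicts with the aim's premise.

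**Perhaps infection is the intended reference.** Section 2.0 says "Many studies have reported the low sensitivity of preoperative urine cultures for predicting infectious complications of urologic stone procedures", and Aim 1 says "The control arm will be utilized to determine if NGS may have predicted infections or high-risk groups". The first is background literature about culture, and the second belongs to Aim 1. Neither is tied to the Aim 2 measures. Nor would a specificity near 50% hide which reference was used: denominators of 20 and 200 would show that it was culture.

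**The positivity terms may look inconsistent.** Section 2.0 says "Of the 18 cultures with no growth, 56% (10/18) did show a dominant-bacteria on NGS" and, later, "NGS identifies a targetable bacterium in up to 50% of negative urine cultures prior to urologic stone surgery". Both sentences describe preliminary work, while Aim 2 keeps to uropathogenic bacteria. Section 8.6 says the NGS report lists the bacteria present, so a laboratory call may exist. What remains is that no organism list or threshold is written down.

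**A careful reader would expect low specificity, since the plan forecasts it.** Partly right: the forecast is open, and the hypothesis can be tested directly. But the plan does not say that its accuracy figures should be read this way.

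**Agreement statistics are the same arithmetic and cannot identify contamination either.** Both statements are true. Positive and negative percent agreement equal sensitivity and specificity numerically, and McNemar's test credits NGS with every extra positive, contaminants included. The gain is that culture is no longer presented as truth and that the paired contrast answers the aim's question.

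**Conclusion.** The concern holds as a conflict within Aim 2: the planned accuracy figures treat as truth a test that the aim says is incomplete. If the hypothesis is met, the report would show specificity of 50% (43% to 57%), PPV of at most 17% and, for a two-level call, AUC of at most 0.75.

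This rests on three things: culture as the implied reference, the plan's counts of 20, 200 and 100, and counting any uropathogen identified by NGS as NGS-positive, which is the rule still to be written.

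A reader might infer that the trial's main result or the Aim 2 hypothesis is compromised. Neither is. The primary infection comparison does not use these figures, and the NGS-positive proportion among culture-negatives can be estimated as planned. The point is worth correcting because a better-suited analysis uses data already to be collected.

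**What to change.** In Aim 2, with matching text in Section 10.0:

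1. State that culture is an imperfect comparator.
2. Fix the NGS-positive rule (organism list or threshold) before results are compared. Do the same for the ROC variable, or drop the AUC against culture.
3. Replace culture-referenced accuracy with paired detection rates (McNemar, with the difference and its interval), positive and negative percent agreement, and the NGS-positive proportion among culture-negatives with its confidence interval.
4. Say plainly that percent agreement equals sensitivity and specificity numerically, and that none of these measures separates true extra detection from contamination.

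Separately, for the Aim 1 statement about the control arm, add an exploratory comparison of 14-day infection by NGS status among culture-negative standard-of-care patients. Their physicians do not see the NGS result, and no positive culture directs their treatment. Use the primary endpoint's infection definition.

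**Cost.** Items 1 to 4 are wording only, since culture and urine NGS are planned for everyone. The exploratory analysis needs written infection criteria, which Sections 8.7, 8.8 and 10.0 do not give, and infection status to day 14, although contact is at about 7 to 14 days. The primary endpoint needs both anyway. Its weakness is few events, about 11 (2 to 15), and hence wide intervals. Section 8.6 also makes antibiotics routine before stone surgery, so these patients receive prophylaxis, which may weaken any association between NGS status and infection.
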